| 
 • Age \geq 18 years • Clinic-confirmed HIV diagnosis • Currently prescribed or eligible for ART • Currently has insurance • Self-reported cocaine use ever • Willing and able to use a cell phone and blister pack for the 12-week intervention | 
 • Unable to provide informed consent • Verbally or physically threatening to research staff • Unable to communicate in either English or Spanish |
|---|--|

2.C. Informed Consent and Enrollment Procedures: All participants must be able to provide informed consent to be enrolled in the study. The RA will obtain informed consent and then explain the purposes, protocol, expectations, and possible risks and benefits of the study.

2.D. Randomization: Although a specific randomization process is not required for pilot RCTs, we want to ensure that crucial covariates that might influence our outcomes are controlled for a priori, especially given the modest sample size proposed in this pilot. Since it has been well-documented that individuals with underlying mental illness experience worse outcomes, we will minimally stratify based on the presence or absence of neurocognitive impairment. Randomization will be 1:1:1:1 to patients receiving either no feedback, automated feedback or automated + clinician feedback, and automated feedback + text-reminder from a social network.

2.E. Study Procedures:

1. Baseline Interview: After the informed consent procedure, participants will be asked to sign a medical release of information (ROI) to allow research staff to confirm self-reports of HIV status, medication prescription and healthcare utilization and to be able to communicate with the participants' clinical providers. The RA will then conduct the baseline interview consisting of various self-reported measures including demographic information, health care status, medical history, standardized measures for drug use and mental illness, and Information Motivation Behavioral (IMB) constructs for adherence. Participants will also undergo phlebotomy.

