 2. Intervention: After randomization, the RA will provide each subject with the following in order to commence the intervention part of the pilot feasibility study: a monthly prescription blister pack and a cell phone (specifically, an Android smartphone). Participants can choose to use their own phones if they already have an Android-based smartphone. The RA will teach the participants how to use blister pack and the smartphone (including using the voicemail and text messaging features).
- RAs will contact the medical providers for prescriptions, which will be sent to the local pharmacy (see section on Smart Pill Box Refills below). The local pharmacy will create medication blister packs. Participants will receive text feedback from the study + text-reminder from social network.

- We will use a text messaging system (Telerivet) to send text reminders to take pills at the dosage time. Information about dosage times will be collected by RA's during the baseline interview time.
-
- We will collect adherence data by counting pills in the blister-pack, a traditional and widely used method in the medication adherence literature. However, instead of manually counting the pills, the participants will take a picture of their blister-pack and text that picture to our study phone number. The participants will send this picture once a week for the intervention period (12 weeks) and the follow-up period (4 weeks). After downloading the pictures from the study phone, we will use image analysis techniques to count the pill(s) in each bin. We will send automated reminders for taking medication and texting the picture.

During the intervention period (12 weeks), a text messaging system (Telerivet) will text all participants once a week on their smartphones to take a brief survey using an app on their smartphones. CommCare is a cloud-based mobile messaging platform that allows a research team to set up an SMS gateway phone. This gateway phone allows the research team to conduct bulk messaging to participants via the telerivet app on one smart phone that has a sufficient data plan. The telerivet app on the gateway phone is directly linked to a Telerivet account that is accessed and managed via the web. The phone number of the participant is loaded into the Telerivet account at baseline, and the Telerivet system is then able to send them automatic reminders on their chosen day via the gateway phone.

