4. Monthly Text-Message Data Collection: At weeks 4, 8, and 12, the following two types of research data will be collected from the participants. A total of 4 text messages (one text message per week) sent by the designated social network member to the participant will be downloaded. The text messages will be downloaded by a RA from the participant's cell phone. In order to pull participant text message/ SMS data off of the project phones, the research team will use a software called *SMS Backup and Restore*. With consent, this software will be installed only on the phones of participants in the fourth arm. The *SMS Backup and Restore* application allows us to connect the text message/SMS data on the participant phones to a secure Dropbox account. Our technical consultant will create these secure Dropbox accounts for every participant phone in the 4th arm and link them to each of the participant's phones. These Dropbox accounts will be protected with a unique password; the only individuals with access to the password and the accounts will be the project staff. During the monthly interviews with participants, the Research Assistants will navigate to the *SMS Backup and Restore* application on the participants' phones and backup the local SMS data to the Dropbox accounts. This is a two-step functionality within the *SMS Backup and Restore* application. The RAs will first click on "Backup" and then will be prompted to choose a location to sync the data to. The RAs will choose to backup the SMS data to the secure Dropbox that will already be linked to the phone. For more details, see the sections on "Risk, Minimizing Risk, and Data and Safety Monitoring Plan".

Individual activities	Time (in weeks)														
	Pre-intervention	Intervention													Follow-up
		0	1	2	3	4	5	6	7	8	9	10	11	12	16
Enrollment	X														
Chart review	X														X
Phlebotomy	X													X	X
Baseline interview	X														
Provide Blister pack		X												X	
Smartphone survey			X	X	X	X	X	X	X	X	X	X	X	X	X
SMS/Text download (only for fourth arm)						X				X				X	
Monthly interviews						X				X				X	X

5. **Subject Population:** Provide a detailed description of the types of human subjects who will be recruited into this study.

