Aim 1 (Focus Groups): We will conduct six FGs, four with HIV+ cocaine users and two with healthcare providers, comprised of 6-8 persons each. For the PLH FGs, we will recruit PLH who primarily use cocaine, from clinical care and community outreach programs in New Haven, CT. Of the four PLH FGs, one will consist solely of men and one solely of women in order to address possible gender differences. Eligibility criteria will be: a) ≥ 18 years; (b) speaks English or Spanish; c) HIV+; d) self-reported cocaine use in the previous 30 days; and e) able to give informed consent. For the two healthcare provider FGs, we will recruit physicians, nurses, clinic supervisors, and substance abuse counselors from HIV clinics. We will target representation from the 5 HIV clinics in New Haven.

Aim 2 (Pilot Feasibility Study): We will recruit 90 participants from HIV care clinics and drug treatment programs in New Haven. Eligibility criteria will include: 1) clinic-confirmed HIV diagnosis; 2) ≥ 18 years; 3) prescribed or eligible (clinician willing to prescribe) for ART; 4) currently have insurance coverage; 5) self-reported cocaine use in the past 6 months; and 6) and willing and able to use an electronic pill box and blister pack for study duration. This will be a 16-week study with a 12-week intervention and 4-week post-intervention observation period.

Sample Size and Power Calculations: The literature suggests that effect size calculations may not be appropriate for pilot RCTs.¹¹⁵ Thus, based on a review of pilot studies that have ranged in sample size from 12 per group¹¹⁶⁻¹¹⁸ to 9%-50%^{119,120} of the proposed larger RCT's sample size (generally 30 per arm); we propose to enroll 20 participants for groups A, B, and C. For Group D, we propose to enroll 30 participants so that hypotheses #7 (There is statistically significant difference between a patient's ART adherence and persistence and HIV outcomes when their designated social network member lives inside vs outside patient's activity space) can be tested. Therefore, a total of 90 study participants for the pilot feasibility RCT is proposed. This sample size is appropriate in order to refine study procedures, develop a final intervention manual and prepare for a future large-scale RCT.

NOTE: Is this research proposal designed to enroll children who are wards of the state as potential subjects? Yes No (If yes, see Instructions section VII #4 for further requirements)

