Aim 2 (Pilot Feasibility Study): The primary outcomes will be ART adherence and persistence, measured as a composite score ranging from 0 to 100%, and as number of continuous days taking ART without a 7-day (or 3-day) gap^{18,71} respectively. Outcome analyses will be conducted for (a) adherence and persistence behavior, (b) drug outcomes (cocaine use), (c) HIV treatment outcomes (VL<20 copies/mL; change in CD4+ T lymphocytes), and (d) ART-related Information, Motivation, and Behavioral Skills constructs. The general framework for discerning differences between study conditions on main outcome variables will be to perform 3 (intervention condition) x 3 (repeated follow-up assessments) mixed design analysis entering pre-intervention scores as covariates and additional theoretically and empirically relevant covariates (such as baseline mental status etc.). For variables that are approximately normally distributed, we will use multivariate analyses of covariance (MANCOVA), with significant multivariate tests followed by subsequent analyses of co-variance (ANCOVA). Variables that violate distributional assumptions of normality will be analyzed using generalized linear model (GLM) procedures, which enable the use of non-Gaussian error models. Based on a review of the literature, GLM is the most appropriate approach for variables with strong positive skew, e.g., adherence.

[figure not shown]
To examine the mediating and moderating effects of activity space and social network facilitators and barriers on primary (ART adherence and persistence) and secondary outcomes (HIV viral suppression, cocaine use, retention in HIV care), the following steps are going to be followed:

- a. A range of variables associated to activity space and social networks (both risk and support) will be calculated using a combination of GIS, SNA, and spatial statistics methods. The variables will be the covariates.
- b. The outcome variables are: primary (ART adherence and persistence) and secondary outcomes (HIV viral suppression, cocaine use, retention in HIV care).
- c. We will first use descriptive statistics, bivariate correlation, and t-tests to understand the distribution and association of all the covariates calculated in step#a with the outcome variables (step#b).
- d. After running tests of multicollinearity, only uncorrelated covariates at $p \leq 0.05$ (considered statistically significant) will be included in the subsequent mediation and moderation analysis.

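### A person with no ART prescription can be randomised, and nothing makes the first blister pack a condition of randomisation, so some participants may have no evaluable primary outcome for part or all of follow-up

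*Combined protocol and SAP*

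**What the plan says.** **Entry.** Section 5, Subject Population (Aim 2), accepts people who are "prescribed or eligible (clinician willing to prescribe) for ART". The inclusion lists under 2.B and in section 7 say "Currently prescribed or eligible for ART". None of the three requires a prescription to exist before randomisation.

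**Order of steps.** Section 2.E, item 2 (Intervention), begins: "After randomization, the RA will provide each subject with the following in order to commence the intervention part of the pilot feasibility study". What is provided is a monthly blister pack and a smartphone. The same item continues: "RAs will contact the medical providers for prescriptions, which will be sent to the local pharmacy". No time limit is given. Dosing times for the reminders are to be collected at the baseline interview.

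**Schedule.** The row "Provide Blister pack" is marked at week 0 and again late in the intervention. Chart review is marked before the intervention.

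**Outcomes and model.** Section 12 (Aim 2) defines adherence and persistence as "measured as a composite score ranging from 0 to 100%, and as number of continuous days taking ART without a 7-day (or 3-day) gap". It states no time zero, no denominator and no rule for a person not yet on ART. The HIV outcomes include viral load below 20 copies/mL and change in CD4 count. The models are specified as "entering pre-intervention scores as covariates", plus further relevant covariates. ART status at entry is not named among them.

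**Stratification.** Section 2.D uses neurocognitive impairment only.

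**The concern.** The hypotheses ask whether feedback improves the taking of prescribed ART. A randomised person who has no pack yet has no pills to count, no dosing time to attach a reminder to and no behaviour for feedback to change. That time is missing for both primary outcomes, and if no pack is ever issued the whole outcome is missing.

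Two further effects arise even when the pack arrives on time. A person never on ART has no pre-intervention adherence score, so the covariate-adjusted model cannot use them without a rule that the plan does not give. A person who starts ART at entry may begin viraemic, so their week-12 viral load and CD4 change partly measure starting treatment, whichever feedback arm they are in.

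The protocol's own background makes such entrants plausible. It says that drug use is associated with clinicians withholding or delaying ART and that people with cocaine use disorders are less often prescribed it. Recruitment also reaches drug treatment centres and a community van.

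**Working it through.** **The plan's own figure.** Three groups of 20 and one of 30: 3 × 20 + 30 = 90, which reproduces the stated total. The plan gives no alpha, power, effect size or standard deviation, so nothing more can be reproduced. I use the stated group sizes of 20 and 30.

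**Inputs that the documents do not give.** These are the share p of entrants not on ART at randomisation and the delay to the first pack. I take p = 5%, 10%, 20% and 30% as an assumed range.

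**How many people.** Expected number among 90 = 90p. Chance of at least one in an arm of 20 = 1 − (1 − p)^20.

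**Chance imbalance.** X and Y are independent binomial counts in two arms of sizes n1 and n2. The probability that |X/n1 − Y/n2| is at least 0.15 is summed exactly.

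| Assumed p | Expected of 90 | At least one in an arm of 20 | Shares differ by ≥15 points, 20 v 20 | Same, 20 v 30 |
|---|---|---|---|---|
| 5% | 4.5 | 0.64 | 0.07 | 0.03 |
| 10% | 9 | 0.88 | 0.18 | 0.10 |
| 20% | 18 | 0.99 | 0.32 | 0.22 |
| 30% | 27 | 1.00 | 0.39 | 0.29 |

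A 15-point difference between arms of 20 is three people (3/20).

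**Upper bound on the effect on the primary outcomes.** This bound assumes that the 12 weeks (84 days) run from randomisation and that days before the pack score zero. The plan does not state such a rule, so this is a worst case and not a prediction. With a delay of d days, persistence cannot exceed 84 − d and adherence cannot exceed (84 − d)/84.

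- 2 weeks: 84 − 14 = 70 days; 70/84 = 83.3%.
- 4 weeks: 84 − 28 = 56 days; 56/84 = 66.7%.
- 6 weeks: 84 − 42 = 42 days; 42/84 = 50.0%.

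Three extra such people in one arm of 20, each delayed 4 weeks, lower that arm's mean ceiling by (3/20) × 33.3 = 5.0 adherence points and (3/20) × 28 = 4.2 persistence days. For scale, with an assumed between-person SD of 25 points the standard error of a 20 v 20 difference is 25 × √(2/20) = 7.9 points. Even in this worst case the shift is less than one standard error.

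**Dilution under the same rule.** Assume a mean of 70 among those on ART, SD 25 and a true difference of 20 points. Power for 20 v 20 is 0.72 with nobody delayed. With 20% delayed it is 0.70, 0.64 or 0.46 at 2, 4 or 8 weeks. It is 0.29 if that 20% never start and are scored zero.

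**If the clock starts at the first pack.** Then d = 0, and the ceilings return to 84 days and 100%. The missing baseline score, the starting-treatment effect on viral load and CD4, and the people who never receive a pack all remain.

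**The case against.** The strongest reply is that the plan already means the pack to start the clock. The intervention text says that the pack is provided in order to begin the intervention, and the schedule marks it at week 0. On that reading, waiting time falls before week 0 and is not part of the 12 weeks. This stands as the evident intention. It does not make the pack a condition of randomisation, and it does not say what happens to someone already allocated whose pack is late or never issued.

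Providers are also contacted so that the pharmacy can pack ART for everyone, including people long on treatment. That is correct: the step does not show that ART is first prescribed after randomisation, only that the plan allows it.

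A reader might infer that both primary outcomes are undefined for these people, or are set by prescribing delay instead of by feedback arm. The documents do not support that. Nothing scores pre-pack weeks as missed doses, and the background section describes non-adherence as departure from a prescription and non-persistence as gaps in treatment. Even under a clock from randomisation, delay caps the outcome and feedback can still act below the cap. A reader might also infer biased arm comparisons. ART status at entry precedes allocation, so randomisation balances it in expectation.

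Baseline viral load and CD4 are measured, and the covariate list is open-ended, so viraemia at entry is partly handled. Baseline adherence for a person never on ART is not.

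Finally, the intervention text refers to a section on pill box refills that is not in the text available for review. It may cover prescription timing.

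**Conclusion.** The point holds as a gap in the randomisation sequence and in the analysis, not as a failure of the primary outcomes. People without a prescription can be allocated. For any time without a pack they contribute no evaluable adherence or persistence. Those never on ART lack the baseline covariate, and those starting at entry bring a treatment-start effect into the viral load and CD4 outcomes.

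The consequences are dilution, added variance, some participants without an evaluable primary outcome, and chance imbalance in small arms. The size is unknown because the documents give neither the share nor the delay. Across an assumed 5% to 30% not on ART, two arms of 20 differ by 15 points or more in that share with probability 0.07 to 0.39 (0.03 to 0.29 for 20 v 30). If the share is near 5% and packs arrive promptly, the effect is small. The ceiling and power figures hold only under a scoring rule that the plan does not adopt, together with an assumed SD, mean and difference. A change is worth making because it is cheap and removes the dependence on these unknowns.

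**What to change.** 1. Keep the eligible pathway, but randomise only when an ART prescription exists and the first blister pack is ready. State this in 2.B, section 5 and section 7, and put the contact with provider and pharmacy before allocation in 2.E.
2. Randomise and hand over the first pack at the same visit, and define that visit as week 0 for the 12-week outcomes. Keeping the two together prevents follow-up from starting before allocation.
3. Report the number screened who never reach a first pack as a feasibility result, so that this information is not lost.
4. Add ART status at screening (on ART, yes or no), taken from the chart review already planned, as a covariate in the adherence, persistence, viral load and CD4 models. For people not previously on ART, let that indicator stand in for the missing baseline adherence score, so that they are not dropped.

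**Cost.** Protocol wording, one extra model term, a short wait between consent and randomisation for some, and a few screened people who are not randomised. The planned total stays at 90, and no new procedure is needed. The change concerns the timing of allocation and the definition of week 0. It does not alter when a clinician prescribes ART.

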- (6) Patients with automated feedback + text-reminder from a social network will have decreased cocaine use compared to patients with only automated feedback and patients with no feedback.
- (7) There is statistically significant difference between a patient's ART adherence and persistence and HIV outcomes when their designated social network member lives inside vs outside patient's activity space.

2. **Background:** Describe the background information that led to the plan for this project. Provide references to support the expectation of obtaining useful scientific data.

Antiretroviral therapy (ART) is extremely effective at reducing morbidity and mortality, and reducing HIV transmission among people living with HIV (PLH).^{1,2} Clinical effectiveness, however, is largely dependent on patients' ART adherence and persistence.³⁻⁹ ART non-adherence and non-persistence substantially reduce viral suppression (VS)¹⁰ and increase HIV transmission risk to others.¹¹⁻¹⁵ Substance use disorders (SUDs) further contribute to poor health outcomes, primarily by reducing ART adherence and persistence.¹⁶⁻²⁰ Cocaine use disorders (CUDs), in particular, result in a number of poor HIV treatment outcomes, including decreased retention in care, poor ART adherence and persistence, low VS, and accelerated HIV progression.²¹⁻²⁸ Considering the high prevalence of CUDs among PLH²⁹⁻³⁴ and the absence of effective medication-assisted therapies (MAT) for treating CUDs, innovative strategies of improving ART adherence in this group are urgently needed.

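### Group D is set at 30 so that hypothesis 7 can be tested, but no effect size, power or inside/outside split supports that, and the contrast is not defined in the analysis plan

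*Combined protocol and SAP*

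**What the plan says.** Under Sample Size and Power Calculations the plan first steps back from formal calculation: "The literature suggests that effect size calculations may not be appropriate for pilot RCTs". It then uses a review of pilot-study sizes, starting at 12 per group, to set three arms: "we propose to enroll 20 participants for groups A, B, and C". Group D has a reason of its own: "For Group D, we propose to enroll 30 participants so that hypotheses #7" can be tested. The section closes "Therefore, a total of 90 study participants for the pilot feasibility RCT is proposed" and calls that number suitable for refining procedures, writing the intervention manual and preparing a larger trial.

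Hypothesis 7 (Statement of Purpose) reads "There is statistically significant difference between a patient's ART adherence and persistence and HIV outcomes" "when their designated social network member lives inside vs outside" the patient's activity space.

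Three other places bear on this:

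- **Section VII, Recruitment Procedures:** each fourth-arm participant gives three names and the research assistant chooses one. No rule refers to where that person lives.
- **2.D. Randomization:** allocation to the four conditions is 1:1:1:1.
- **12. Statistical Considerations, Aim 2:** "The general framework for discerning differences between study conditions on main outcome variables" is a 3 x 3 mixed design by condition and follow-up, with pre-intervention scores as covariates. A separate list of steps derives activity-space and social-network variables, relates them to the outcomes by correlations and t-tests, screens them, and enters them in structural equation models.

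**The concern.** Ten of the 90 places rest on one comparison, and that comparison is between two subgroups inside one arm. Their sizes depend on whom participants name and whom the assistant picks, so an even split is the best case and not the expected one. Even then each side has 15 people, fewer than the 20 in each of the other arms.

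The hypothesis is worded as a significance claim, but nothing shows that 30 people can support one. The analysis section does not say how inside and outside are determined, that the comparison is confined to Group D, or which outcome carries it, although hypothesis 7 covers adherence, persistence and HIV outcomes.

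Two things are at stake. A non-significant result might be taken to mean that the designee's location is unimportant when the interval still allows a substantial difference. And an undefined contrast over several outcomes leaves room to choose what to report.

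**Working it through.** **The plan's own figure.** The total reproduces: 3 x 20 + 30 = 90. The 30 for Group D cannot be reproduced, because no effect size, SD, power, significance level or split is given for hypothesis 7.

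**Inputs**

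- From the plan: 30 in Group D.
- Significance level: 5%. This is the only threshold in the plan, given for covariate screening and not for hypothesis 7.
- Assumed: two-sided test, since the hypothesis has no direction; 80% power; SD = 1; no dropout; splits from 15/15 to 24/6.

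**Formulas**

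- Standard error of the difference, in SD units: se = sqrt(1/n1 + 1/n2).
- 95% CI half-width: t(0.975, n1 + n2 - 2) x se.
- Detectable difference: the d at which noncentral-t power, with noncentrality d/se, equals 80%. The normal approximation is (1.960 + 0.842) x se.

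At 15/15, se = sqrt(2/15) = 0.365. The half-width is 2.048 x 0.365 = 0.75 SD. The normal approximation gives 2.802 x 0.365 = 1.02 SD and the noncentral t gives 1.06 SD.

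| Split | se | 95% CI half-width (SD) | Difference at 80% power (SD) | Power at 0.5 SD | Power at 0.8 SD |
|---|---|---|---|---|---|
| 15/15 | 0.365 | 0.75 | 1.06 | 26% | 56% |
| 20/10 | 0.387 | 0.79 | 1.12 | 24% | 51% |
| 24/6 | 0.456 | 0.93 | 1.32 | 18% | 39% |

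**What the extra ten buy.** With 20 in Group D split 10/10, the detectable difference is 1.32 SD. Going to 30 brings the best case to 1.06 SD.

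**Size needed.** 80% power takes 64 per subgroup at 0.5 SD, 26 at 0.8 SD and 17 at 1.0 SD (noncentral t).

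**Baseline adjustment.** With one covariate at 15/15 (27 degrees of freedom), the detectable difference is 1.061 x sqrt(1 - r^2). The plan gives no r. Assumed values give 1.01 SD (r = 0.3), 0.92 SD (r = 0.5) and 0.76 SD (r = 0.7).

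**Binary outcome.** For viral suppression of 80% versus 50% (assumed) at 15/15, Fisher's exact test has 25% power by enumeration.

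**Attrition and allocation.** If six are lost and the rest split 12/12, the detectable difference is 1.20 SD. Allocation at 1:1:1:1 gives 90/4 = 22.5 per arm; 12/11 or 11/11 then gives about 1.23 to 1.26 SD and a half-width of about 0.87 to 0.89 SD.

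**The case against.** The strongest reply is that this is a pilot, that the plan declines effect-size calculations, and that it says only that hypothesis 7 can be tested, not that it is powered. A 15/15 split also meets the 12-per-group figure that the plan cites. This stands in part: the fault is an unsupported justification, not a miscalculation. It does not remove the problem, because the plan makes an exception for Group D and ties it to a claim of statistical significance.

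Four stronger readings are tempting, and the documents do not support them.

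- **That no planned analysis could make the comparison.** The Aim 2 steps include t-tests of activity-space and network variables against the primary and secondary outcomes, and an inside/outside indicator would fit there. What is missing is its definition, the restriction to Group D and the link to hypothesis 7.
- **That differences below 1 SD cannot be detected.** The 1.06 SD is an 80%-power threshold for an unadjusted test. At 15/15 an observed difference of about 0.75 SD already gives p < 0.05, and adjustment can bring the threshold below 1 SD. The plan states baseline adjustment only for the comparison of conditions, however, and gives no correlation.
- **That non-significance is the likely result even for a large effect.** At 15/15, power is 56% at 0.8 SD and 75% at 1.0 SD. The statement fits a moderate effect, the binary example above, or 0.8 SD at 24/6.
- **That the lack of direction is a defect.** A two-sided question is legitimate. Only the words about statistical significance are out of place in a hypothesis.

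**Conclusion.** The stated reason for 30 in Group D is not supported by the design. Under an unadjusted two-sided 5% test with no dropout, the most favourable split has 80% power only at about 1.06 SD, and the uneven splits examined need up to 1.32 SD. With an assumed baseline correlation of 0.5 to 0.7 the best case is about 0.92 to 0.76 SD, which is still a large difference. The 95% CI half-width, 0.75 to 0.93 SD over the splits shown, describes what 30 people can deliver. These figures rest on assumed splits and, for the adjusted values, assumed correlations.

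The contrast is under-specified rather than absent from the analysis plan. The 1:1:1:1 ratio would put about 22 to 23 of 90 in Group D, so the 30 is itself in conflict with the randomization section. This is a should-fix: the trial is a pilot, hypothesis 7 is the last of seven, and wording settles the point, but the wording changes what may be concluded.

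**What to change.** 1. **Sample Size and Power Calculations.** State that the 30 in Group D is for exploratory estimation of the inside-minus-outside difference. Give the expected unadjusted 95% CI half-width for a range of splits: about 0.75 SD at 15/15, 0.79 SD at 20/10 and 0.93 SD at 24/6, before dropout. Say that the split is not controlled.
2. **Hypothesis 7.** Reword it without reference to statistical significance, both in the Statement of Purpose and where the sample-size section repeats it.
3. **Statistical Considerations, Aim 2.** Define the inside/outside indicator from the baseline activity-space data. Within Group D, estimate the inside-minus-outside difference in adherence, persistence and the HIV outcomes, adjusted for the baseline value where one is collected, each with a 95% CI and no significance claim. Link this to hypothesis 7.
4. **Randomization.** Reconcile the 1:1:1:1 ratio with 20/20/20/30. If the ratio stays and Group D has 22 to 23 people, the half-widths in item 1 must be recalculated (about 0.87 to 0.89 SD at a near-even split).

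Cost: text changes and no extra participants. The downside is that the case for 30 rather than 20 in Group D looks weaker once its precision is stated.
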